### 8.3.2 Vital Signs

Vital signs measurements will include supine blood pressure (after 5 minutes in supine position), pulse rate, respiratory rate, and body temperature.

The Investigator will determine if any of the vital signs measurements are clinically significant or not clinically significant.

See Schedule of Activities (Section 1.2) for the timing and frequency. Vital signs will be assessed every 30 minutes during an infusion. For infusions <35 minutes, vital signs assessments may occur at the beginning and end of infusion.

#### 8.3.3 12-Lead ECG

Triplicate (3 ECGs within a 10-minute period) 12-lead ECGs will be obtained after the subject has been in the supine position for at least 5 minutes. Electrocardiogram assessments will include comments on whether the tracings are normal or abnormal, rhythm, presence of arrhythmia or conduction defects, morphology, any evidence of myocardial infarction, or ST segment, T Wave, and U Wave abnormalities. In addition, the following intervals will be measured and reported: RR, PR, QRS, and QTc.

The Investigator will determine if the ECG results are clinically significant or not clinically significant.

See Schedule of Activities (Section 1.2) for the timing and frequency.

#### 8.3.4 Physical Examinations

A complete physical examination will include assessments of the head, eyes, ears, nose, throat, skin, thyroid, neurological, lungs, cardiovascular system, abdomen (liver and spleen), lymph nodes, and extremities. Height and weight will also be measured.

An abbreviated physical examination will include assessments of skin, lungs, cardiovascular system, and abdomen (liver and spleen).

Compound: M254 Protocol: MOM-M254-001

Protocol Date and Version:8 Global 28 April 2020

See Schedule of Activities (Section 1.2) for the timing and frequency.

#### **8.3.5** Infusion Reaction Evaluation

Systemic infusion reactions are not uncommon with administration of biologics and in particular with therapeutic antibodies, including IVIg, as described below.

The Investigator will evaluate and record the signs and symptoms of infusion reactions as individual AEs. All systemic infusion reactions and associated AEs will be graded using CTCAE. The occurrence of a moderate or severe systemic infusion reaction should prompt a meeting of the SRC to review the clinical circumstances and make a determination as to whether dosing should continue.

Premedication prior to M254 administration should not be administered systematically.

Most systemic infusion reactions are either acute or subacute, occurring within 24 hours of the infusion. Delayed reactions are less common; by definition these occur more than 24 hours after the infusion; in practice most occur 5 to 10 days after the infusion [25]. Infusion reactions are often described in terms that are related to a presumed mechanism (eg, allergic, IgE mediated, immune complex mediated, target-engagement mediated, cytokine release, anaphylactic, anaphylactoid); in practice, determination of mechanism is often challenging and based on observation, course, laboratory assessments, and expertise. Acute infusions should be classified as mild moderate or severe. Mild reactions may present with flushing, dizziness, diaphoresis, nausea, palpitations, and hyperemia. Moderate reactions may present with chest pain, hypertension, hypotension, fever, urticaria, dyspnea, chills, and/or rash. Severe reactions may present with marked hypertension or hypotension, severe dyspnea, bronchospasm, stridor, wheezing, and rigors. Most reactions tend to be mild, and related to the rate of the infusion [25], and can be managed by slowing or temporarily stopping the infusion. If necessary, antihistamines or acetaminophen may be given according to the clinical judgment of the Investigator. With moderately severe acute reactions, the infusion should be discontinued, and the subject should be treated with acetaminophen and antihistamines, and if necessary with corticosteroids. Once the reaction has been arrested, the infusion may be cautiously restarted, if deemed appropriate by the Investigator. With severe reactions the infusion should be discontinued, and the subject should be treated immediately with acetaminophen, antihistamines, and systemic corticosteroids. If anaphylaxis if present, epinephrine should be administered before the corticosteroids. The infusion should not be restarted even if the reaction is brought under control.

Delayed reactions (after 24 hours) most likely represent a mild type III immune complex reaction, typically secondary to anti-drug antibodies. The most common symptoms that have been reported associated with delayed reactions include joint pains, rash, arthritis, myalgia, jaw pain, fatigue, headaches, edema, sore throat, and fever. If the symptoms are mild, acetaminophen alone may be sufficient. Persistent severe symptoms may require a short course of corticosteroids, and discontinuation of further study drug administration.

Compound: M254 Protocol: MOM-M254-001

Protocol Date and Version:8 Global 28 April 2020

### **8.3.6** Clinical Safety Laboratory Assessments

See Appendix 2 for the list of clinical laboratory tests to be performed and to the Schedule of Activities (Section 1.2) for the timing and frequency.

The Investigator must review the laboratory report, document this review, and record any clinically relevant changes occurring during the study in the AE section of the eCRF. The laboratory reports must be filed with the source documents. Clinically significant abnormal laboratory findings are those which are not associated with the underlying disease, unless judged by the Investigator to be more severe than expected for the participant's condition, and will be considered AEs.

All laboratory tests with values considered clinically significantly abnormal during participation in the study should be repeated until the values return to normal or baseline or are no longer considered clinically significant by the Investigator. If such values do not return to normal/baseline within a period of time judged reasonable by the Investigator, the etiology should be identified and the sponsor notified.

Subjects will be in a seated or supine position during blood collection. Instructions for blood collection, processing, storage, and shipping are described in the Laboratory Manual.

## 8.3.7 Pregnancy Screen

A serum pregnancy test will be conducted at screening and on Day 29 for all female participants of childbearing potential. A urine pregnancy test will be conducted on Day -1.

#### 8.4 Adverse Events and Serious Adverse Events

The definitions of an AE or SAE can be found in Appendix 3.

Adverse event(s) may be reported by the participant (or, when appropriate, by a caregiver, surrogate, or the participant's legally authorized representative) or by the Investigator.

The Investigator and any qualified designees are responsible for detecting, documenting, and recording events that meet the definition of an AE or SAE and remain responsible for following up AEs that are serious, considered related to the study intervention or study procedures, or that caused the participant to discontinue the study (see Section 7).

#### 8.4.1 Time Period and Frequency for Collecting AE and SAE Information

All SAEs will be collected from the time of consent until the end of study at the time points specified in the Schedule of Activities (Section 1.2).

All AE will be collected from the time of consent until the end of study at the time points specified in the Schedule of Activities (Section 1.2).

Compound: M254 Protocol: MOM-M254-001

Protocol Date and Version:8 Global 28 April 2020

All SAEs will be recorded and reported to the sponsor or designee immediately and under no circumstance should this exceed 24 hours from becoming aware of the event, as indicated in Appendix 3. The Investigator will submit any updated SAE data including but not limited to previously missing information, corrections, or additional details of the event, to the sponsor or designee within 24 hours of the Investigator becoming aware.

Investigators are not obligated to actively seek information about AEs or SAEs occurring after conclusion of the study participation. However, if the Investigator learns of any SAE, including a death, at any time after a participant has been discharged from the study, and he/she considers the event to be reasonably related to the study intervention or study participation, the Investigator must promptly notify the sponsor.

## 8.4.2 Method of Detecting AEs and SAEs

The method of recording, evaluating, and assessing causality of AE and SAE and the procedures for completing and transmitting SAE reports are provided in Appendix 3.

Care will be taken not to introduce bias when detecting AEs and/or SAEs. Open-ended and nonleading verbal questioning of the participant is the preferred method to inquire about AE occurrences.

## 8.4.3 Follow-up of AEs and SAEs

After the initial AE/SAE report, the Investigator is required to proactively follow each participant at subsequent visits/contacts. All SAEs and nonserious AEs of special interest (systemic infusion reactions, hemolysis, infections, flu-like symptoms, rash, myalgia and arthralgia, fever, chills), will be followed until resolution, stabilization, the event is otherwise explained, or the participant is lost to follow-up (as defined in Section 7.3). Further information on follow-up procedures is given in Appendix 3.

### 8.4.4 Regulatory Reporting Requirements for SAEs

- Prompt notification by the Investigator to the sponsor of an SAE is essential so that regulatory obligations and ethical responsibilities towards the safety of participants and the safety of a study intervention under clinical investigation are met.
- The sponsor has a legal responsibility to notify both the local regulatory authority and other regulatory agencies about the safety of a study intervention under clinical investigation. The sponsor will comply with country-specific regulatory requirements relating to safety reporting to the regulatory authority, IRB/IEC, and Investigators.
- Investigator safety reports must be prepared for suspected unexpected serious adverse reactions according to local regulatory requirements and sponsor policy and forwarded to Investigators as necessary.
- An Investigator who receives an Investigator safety report describing a SAE or other specific safety information (eg, summary or listing of SAEs) from the sponsor will

Compound: M254 Protocol: MOM-M254-001

Protocol Date and Version:8 Global 28 April 2020

review and then file it along with the Investigator's Brochure and will notify the IRB/IEC, if appropriate according to local requirements.

## 8.4.5 Pregnancy

- Details of all pregnancies in female participants and, if indicated, female partners of male participants will be collected after the start of study intervention and until 30 days after the final study visit.
- If a pregnancy is reported, the Investigator should inform the sponsor or designee within 24 hours of learning of the pregnancy and should follow the procedures outlined in Appendix 4.
- Abnormal pregnancy outcomes (eg, spontaneous abortion, fetal death, stillbirth, congenital anomalies, ectopic pregnancy) are considered SAEs.

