## 4.1.4 Part D (USA sites included)

Part D is a repeated, fixed-dose, open-label study of M254. Any patients who participate in Parts B or C are allowed to participate in Part D if they meet inclusion criteria during screening for Part D. Part D may have up to 2 dose levels with up to approximately 15 to 34 ITP patients in total. The initial dose level for Part D will be less than or equal to the maximum tolerated dose, and it will be selected based on review of Part B data and available data from Part C. Following completion of Part C, the dose for new patients in Part D may be revised (the dose level will not be modified for patients who have already received at least 1 dose). Patients who have participated in Part B or C may be allowed to participate in Part D, prior to completion of randomization in Part C. New patients not in Part B or C may participate in Part D following complete randomization in Part C. The dose levels of M254 for Part D will be determined after analysis of available data from Part A, Part B, and Part C.

Following screening to confirm eligibility to participate (including rescreening patients who participated in Part B or C), M254 naïve patients will receive 4 doses of M254, and patients from Part B or C will receive 3 doses of M254 every 14 days. Patients in Part C may roll over into Part D by including any data after the last dose of IVIg or M254 in Part C for assessment of screening in Part D as long as those data are within the screening window specified. Please refer to Section 4.3.1 and Figure 1-5 for dosing details.

If the patient's platelet count has not returned to  $\leq 100 \times 10^9 / L$ , their platelet count will be monitored weekly until platelets return to  $\leq 100 \times 10^9 / L$ . If these conditions are not met, M254 will not be administered further. Patients will be followed for safety assessments and platelet counts up to at least 28 days post their last dose of M254. Safety will be reviewed by the SRC quarterly (or more often as required).

Blood for safety labs, PK, and PD will be collected as defined in the Schedule of Activities (Table 1-4).

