## b. Female participants:

- A female participant is eligible to participate if she is not pregnant (see Appendix 4), not breastfeeding, and at least 1 of the following conditions applies:
  - Not a WOCBP as defined in Appendix 4 (surgically sterilized via hysterectomy, bilateral oophorectomy, or bilateral tubal ligation) or of nonchildbearing potential (ie, postmenopausal for at least 1 year).

OR

- A WOCBP who agrees to follow the contraceptive guidance in Appendix 4 during the treatment period and for at least 90 days after the last dose of study intervention (ie, study completion or premature discontinuation from the study).
- Of childbearing potential, with a fertile male sexual partner, willing to use 2 adequate methods of contraception for 2 weeks prior to administration of study medication, during study treatment, and for 90 days following the last treatment (ie, study completion or premature discontinuation from the study). Adequate contraception is defined as using hormonal contraceptives or an intrauterine device combined with at least 1 of the following forms of contraception: a diaphragm or cervical cap, or a condom. Also, total abstinence, in accordance with the lifestyle of the subject, is acceptable.
- 9. If female, a negative serum pregnancy test at screening and a negative urine pregnancy test at check-in to the clinic for the baseline visit, and not nursing or planning a pregnancy through 90 days following the last dose of study medication.
- 10. Subject is capable of giving signed informed consent as described in Appendix 1 which includes compliance with the requirements and restrictions listed in the ICF and in this protocol.
- 11. Prothrombin time (PT) and activated partial thromboplastin time ≤1.4-fold above the upper limit of normal.

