#### 8.1.3 Follow-up

A follow-up visit will be completed  $29 \pm 2$  days after the last dose of study drug for Parts A, B, and C. For Part D, the follow-up visit will be completed  $71 \pm 3$  days (M254 naïve patients) or  $57 \pm 3$  days (Part B/C patients). Refer to the Schedule of Activities (Section 1.2) for required procedures during this visit.

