# **Contraception Guidance:**

# Male Participants

Male participants are eligible to participate if they agree to the following during the intervention period and for at least 100 days after the last dose of study intervention:

Refrain from donating sperm

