# **Pregnancy Testing:**

- Women of childbearing potential should only be included after a confirmed menstrual period and a negative highly sensitive serum pregnancy test.
- Additional pregnancy testing is required during Day 1 of the treatment period and at follow-up visit, corresponding to protocol-defined time frame in Section 5.1 after the last dose of study intervention and as required locally.
- Pregnancy testing will be performed whenever a menstrual cycle is missed or when pregnancy is otherwise suspected.

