# **Collection of Pregnancy Information**

# Male participants with partners who become pregnant

- The Investigator will attempt to collect pregnancy information on any male participant's female partner who becomes pregnant while the male participant is in this study. This applies only to male participants who receive study intervention.
- After obtaining the necessary signed informed consent from the pregnant female partner directly, the Investigator will record pregnancy information on the appropriate form and submit it to the sponsor within 24 hours of learning of the partner's pregnancy. The female partner will also be followed to determine the outcome of the pregnancy. Information on the status of the mother and child will be forwarded to the sponsor. Generally, the follow-up will be no longer than 6 to 8 weeks following the estimated delivery date. Any termination of the pregnancy will be reported regardless of fetal status (presence or absence of anomalies) or indication for the procedure.

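### Required pregnancy collection ends about 58 days after the last dose on the nominal schedule, short of the protocol's own contraception periods of 90 days (women) and 100 days (men)

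*Protocol*

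**What the plan says.** **Collection.** Protocol Section 8.4.5 covers female participants and, if indicated, female partners of male participants. Details "will be collected after the start of study intervention and until 30 days after the final study visit". The section then sends the investigator to Appendix 4 for procedures. Appendix 4 is narrower: it covers a woman who conceives during her own participation, and a partner "who becomes pregnant while the male participant is in this study".

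**Contraception.** Section 5.2.1 requires women of childbearing potential to follow the contraceptive guidance "during the treatment period and for at least 90 days after the last dose of study intervention", and not to plan a pregnancy over the same 90 days. Appendix 4 requires male participants to comply "for at least 100 days after the last dose of study intervention".

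**Final visit.** Section 8.1.3 sets it at 29 ± 2 "days after the last dose of study drug for Parts A, B, and C". Tables 1-2 and 1-3 show Day 29 ± 3. For Part D, Section 4.1.4 states: "Patients will be followed for safety assessments and platelet counts up to at least 28 days post their last dose of M254".

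**Testing.** Section 8.3.7 states: "A serum pregnancy test will be conducted at screening and on Day 29". Appendix 4 asks for a test "at follow-up visit, corresponding to protocol-defined time frame in Section 5.1 after the last dose of study intervention". No Schedule of Activities has a pregnancy test after the final visit.

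**The concern.** The protocol asks participants to avoid pregnancy for 90 or 100 days after the last dose, but stops requiring sites to collect pregnancies well before then. A pregnancy beginning on day 70, for example, lies inside both contraception periods and outside the collection window. If it runs a normal course, nothing clearly requires the site to record it or follow it to outcome.

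M254 is a first-in-human product and pregnancy is excluded at entry. Information on pregnancy exposure can therefore come only from pregnancies that arise after dosing starts, and part of that small yield would not be captured systematically.

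There is also an internal conflict. Section 8.4.5 and Appendix 4 give different end points, so a site cannot be sure whether a pregnancy that begins shortly after the final visit is to be collected. The testing sentence in Appendix 4 points to Section 5.1, the healthy-volunteer criteria, although ITP patients enter under Section 5.2. The 90-day time frame there matches no scheduled test.

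**Working it through.** **Step 1. Last dose to final visit (V).**
- Parts A, B and C (Tables 1-1 to 1-3): Day 29 − Day 1 = 28 days.
- Part D, M254-naïve (Tables 1-4 and D2): Day 71 − Day 43 = 28 days.
- Part D, from Part B or C: Day 57 − Day 29 = 28 days.

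This reproduces the 28 days that Section 4.1.4 states for Part D.

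**Step 2. Formulas.** Collection ends on day E = V + 30 after the last dose. The uncovered period is 90 − E days for women and 100 − E days for partners of men.

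| Case | V | E | Women: days of 90 | Men: days of 100 |
|---|---|---|---|---|
| Nominal schedule | 28 | 58 | 32 (35.6%) | 42 (42.0%) |
| Section 8.1.3 read literally | 29 | 59 | 31 (34.4%) | 41 (41.0%) |
| Visit 3 days early | 25 | 55 | 35 (38.9%) | 45 (45.0%) |
| Visit 2 days late | 30 | 60 | 30 (33.3%) | 40 (40.0%) |
| Visit 3 days late | 31 | 61 | 29 (32.2%) | 39 (39.0%) |
| Follow-up to Day 57 | 56 | 86 | 4 (4.4%) | 14 (14.0%) |

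The last row applies when platelets are slow to return to near baseline and follow-up is extended (Sections 4.1.2 and 4.1.3).

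**Step 3. The same count from the M254 dose when IVIg is given last.** This covers everyone who completes Part B and the M254/IVIg sequence in Part C. With crossover on Day 29, collection runs to 28 + 28 + 30 = 86 days after M254, leaving 90 − 86 = 4 days and 100 − 86 = 14 days. With crossover on Day 57 it runs to 56 + 28 + 30 = 114 days, which is past both periods. Among the parts still open, the full nominal gap after M254 therefore falls on the IVIg/M254 sequence of Part C and on Part D.

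**Step 4. Is there other text that closes the gap?**
- Section 8.4.1 says investigators need not seek events after participation ends, but must notify the sponsor if they learn of an SAE they consider reasonably related.
- Appendix 4 has the same passive rule for pregnancy-related SAEs after the study. It also says that a pregnancy in itself is neither an AE nor an SAE.
- Appendix 4 calls for testing when a period is missed or pregnancy is suspected, with no end date, but adds no collection window.

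None of these extends required collection to 90 or 100 days.

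**The case against.** **Adverse outcomes keep a route.** Section 8.4.5 classes abnormal outcomes such as spontaneous abortion, stillbirth and congenital anomaly as SAEs, and related SAEs learned of after the study must be reported. Its instruction to inform the sponsor within 24 hours once a pregnancy is reported carries no end date of its own. This stands. A reader might infer that a conception on day 70 leads to no report and no follow-up at all, and the documents do not support that. The remaining route is passive and limited to events judged related, so other pregnancies are still missed.

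**The gap is not uniform.** This stands too. A reader might infer that more than a third of the period is always uncovered. For women it is exactly one third if the visit is 2 days late, less if it is 3 days late, and about 4 days with follow-up to Day 57. Patients whose last dose is IVIg are covered to at least about day 86 after M254. However, the protocol counts contraception from the last dose of any study intervention, so the mismatch in wording remains for them.

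**Contraception periods are not labelled surveillance periods.** Correct. Treating 90 and 100 days as the protocol's risk period is an inference. Appendix 4 mentions a period of risk when defining abstinence, but gives it no number.

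**Appendix 4's wording suggests a larger gap.** Read alone it would leave 90 − 28 = 62 days of 90 and 100 − 28 = 72 of 100. The documents do not support that as the size, because Section 8.4.5 sets an explicit window and cites Appendix 4 for procedures. The two texts do still need to agree.

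**Few pregnancies are expected.** Take the failure rate in Appendix 4 (under 1% a year) and assume, generously, that all 74 patients are fertile women: 74 × 32/365 × 0.01 ≈ 0.065 pregnancies. Typical-use failure may be higher, as Appendix 4 notes. This keeps the priority low but does not remove the inconsistency.

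**Unseen documents.** The consent forms and the Safety Management Plan are not available here and may already tell participants how long to report.

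**Conclusion.** The mismatch is real and is a cheap improvement. As written, required pregnancy collection ends nominally 58 days after the last dose (55 to 61 across the ±3-day window). That leaves 32 of 90 days uncovered for women (36%; 32% to 39%) and 42 of 100 days for partners of men (42%; 39% to 45%). The gap is about 4 and 14 days when follow-up runs to Day 57 or, counted from M254, when IVIg is given last on Day 29. What is lost is required reporting and outcome follow-up of pregnancies other than related SAEs that happen to come to light.

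A reader might infer that these late pregnancies are the only human exposure data the trial can give. The documents do not support that, since pregnancies up to about day 58 are collected.

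The figures assume that both periods run from the last dose of study intervention. Section 5.2.1 also glosses that point as study completion. Counted from there the uncovered part would be larger: 90 − 30 = 60 days of 90 and 100 − 30 = 70 of 100. No endpoint or planned analysis is affected.

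**What to change.** Reconcile Section 8.4.5 and Appendix 4 to one collection window that matches the contraception periods already in the protocol:
- female participants: from the start of study intervention to 90 days after the last dose;
- partners of male participants: from the start of study intervention to 100 days after the last dose.

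State once, in the same words in both places, that the count runs from the last dose. At the final visit, tell participants to report any pregnancy up to that date. Correct the Appendix 4 testing cross-reference so that it agrees with the scheduled tests. Section 8.3.7 and the Part D footnote, which name Day 29, should likewise be aligned with the Part D table, which puts the last test at Day 71 or Day 57.

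The change concerns Parts B to D, because Part A is complete. It costs protocol and consent wording, plus accepting participant-initiated reports for about 5 to 6 more weeks (32 and 42 days). No visit or test is added, and contraception and dosing rules stay as they are.
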